12.7. Safety methods

When an adverse reaction is discovered, the researcher can take necessary treatment measures, such as medication or surgical intervention, according to the situation, and decide whether to suspend the trial. In the event of a serious adverse event, the unit undertaking the trial and research must take necessary measures to protect the safety of the subjects.

13. Drop-outs

13.1. Dropout determination

Participants who withdraw from the trial for any reason will be considered a drop-out.

13.2. Common reasons for dropping out

- Poor compliance with the protocol
- Adverse events
- Lack of efficacy
- Withdraw and quit
- Others

13.3. Dropout management

Physicians should complete the case report form and record the reason for dropping out. Physicians should also assess the causal-effect relationship of the intervention with adverse events and collect detailed data related to the last exercise session. The data from subjects who have dropped out will be stored and used for intention-to-treat analysis

14. Ethical requirements

The study followed the ethical guidelines of the Helsinki Declaration and obtained the approval of the Ethics Committee of Zhujiang Hospital of Southern Medical University (ratification No.:2018-NFMDXK-001), the host research unit, and complete registration at the China Clinical trial Registration Center (registration number: ChiCTR1800015156).

15. Data management

15.1. Case report form

All case report forms for each participant should be filled out by study staff in a timely manner. The case report form should be double-checked for potential errors or missing data prior to patients leaving the clinic. All data, including screening assessments, questionnaires, physical examinations, and laboratory examinations, will be filed in the participant's chart. Original documents, participants' charts, and CRF forms will be stored in the study office

15.2. Data entry

All data will be double-entered by researcher staff. Two sets of databases will be generated and tested for consistency using the SAS program. Whenever inconsistencies are found, the data will be corrected by re-examination of the original case report forms or laboratory reports.

15.3. Data reports

Several standardized reports will be generated as follows: 1) participant recruitment and follow-up; 2) demographics; 3) data quality and monitoring; 4) adverse events. These reports will be used for study management. These reports will be blinded to research personnel who collect study outcomes.

16. Data Analysis Plan

Data will be analyzed according to participants' randomization assignments, regardless of their subsequent status (intention-to-treat).

16.1. Study outcomes

The primary outcome is change of body mass index (BMI). The secondary outcomes included changes in body weight, body fat, waist circumference and metabolic risk factors.

16.2. Analysis methods

Data will be analyzed according to participants' randomization assignment (intent-to treat). A mixed-effects model will be used to assess the effects of diet programs on the change in BMI and an autoregressive correlation matrix will be used to correct within-participant correlation for repeated measurements. In this model, variables will be assumed to be random effects, and intervention group, time, and their 2-factor interactions, age, sex will be assumed to be estimable fixed effects. PROC MIXED of SAS statistical software, version 9.4 (SAS Institute Inc), will be used to obtain point estimates and SEs of the treatment effects and to test for differences between treatments. Multiple imputations for missing data in the multivariable analyses will be conducted using the Markov chain Monte Carlo method. P-value <0.05 will be considered as statistically significance. Group differences in the study outcomes will be evaluated using the general linear model for continuous variables and the chi-squared test for categorical variables. Data will be presented as least-squares means with 95% confidence intervals (CIs).

17. Training for Study Staff

All study staff (physicians and nurses) will be trained and certified before the study is initiated. The training program will include instruction on questionnaire administration and anthropometrics (height, weight, waist circumference, and hip girth) and blood pressure measurement. A standard questionnaire will be used, which includes personal information (name, sex, age, place of birth, marital status, occupation, education, household income, etc.), medical history, medication use, family history, lifestyle factors (smoking and drinking), physical activity, dietary habits, and menstrual and reproductive history. Anthropometric measurements and blood pressure will be obtained using a standard protocol. The data, including that for dietary record, duration, heart rate, and anthropometric measurements, will be collected and recorded in CRFs by research assistants every week. Body fat mass will be quantified using a body composition analyzer (Jawon Medical, Gyeongsansi, South Korea). All technologists are experienced and blind to randomization of the participants.

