7.2. Intervention monitoring and quality control

All the food consumption and exercise will be supervised by research assistants. The types of foods, amount of food and cooking methods, will be recorded by participants themselves. Nutrient intake will be estimated every 4 weeks, at baseline and 4-, 8- and 12-week. In order to reduce impacts caused by exercise, participants will be instructed not to change their daily physical activity and record their regular physical activity by wearing a Mi Band 2 Smart Bracelet (Xiaomi, Beijing, China) and record macronutrients, nutrition labels and detailed dietary recipes. Research assistants will call participants twice weekly to assess their compliance and provide advice on adherence to the dietary program. Adherence to the dietary program was

defined according to the number of days that a participant met the requirements of the assigned diet.

8. Study Outcomes

8.1. Primary outcome:

Changes in BMI from baseline at 12 weeks after intervention.

8.2. Secondary outcomes:

- Changes in body weight, waist circumference, WHR and body fat
- Changes in lipid and glucose
- Changes in insulin resistance
- Changes in urinary albumin and liver enzyme

9. Participant Termination and Retention

9.1. 9.1 Termination criteria

- Adverse events or other unexpected reasons (e.g., hypoglycaemia, constipation, gastrointestinal discomfort, etc.)
- Inability to complete required dietary program
- Unwillingness to be followed-up

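### The autoregressive structure fixed for the primary model can misstate the week-12 standard error unless visit variances behave as it assumes; an unstructured covariance removes that dependence

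*Protocol*

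**What the plan says.** The primary outcome in Protocol section 8.1 is "Changes in BMI from baseline at 12 weeks after intervention". Section 3.2 compares it between any two of the four groups. Height and weight are measured at weeks 4, 8 and 12 (sections 11.4 to 11.6), and section 11.3 also lists them under the week 0 visit.

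Section 16.2 sets out the model:
- Purpose: "A mixed-effects model will be used to assess the effects of diet programs on the change in BMI".
- Within-participant structure: "an autoregressive correlation matrix will be used to correct within-participant correlation for repeated measurements".
- Fixed part: "intervention group, time, and their 2-factor interactions, age, sex will be assumed to be estimable fixed effects".
- Random part: "In this model, variables will be assumed to be random effects", with no variable named.
- Inference: PROC MIXED "will be used to obtain point estimates and SEs of the treatment effects and to test for differences between treatments".

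Later in the same section: "Group differences in the study outcomes will be evaluated using the general linear model for continuous variables".

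The section does not say whether the variances may differ between visits, whether a robust standard error will be used, or what replaces the autoregressive structure if it fits badly. It also does not say whether the repeated response is the change score at weeks 4, 8 and 12, or BMI at weeks 0, 4, 8 and 12 with change taken as a contrast.

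**The concern.** The ordinary autoregressive structure, AR(1), has one variance for all visits and a correlation that decays with the distance between visits. Change from baseline is zero at week 0 by construction, and participants on different diets with different adherence can be expected to drift apart. If the spread is smaller at week 4 than at week 12, a common variance averages the small early variances into the week-12 standard error and makes it too small.

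The trial's conclusion rests on the week-12 contrasts, so this one modelling choice would carry straight into the primary P values. A Bonferroni correction would not repair it, because each adjusted test would use the same standard error.

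**Working it through.** **Inputs from the protocol.** Four groups, hence 4 × 3 / 2 = 6 pairs; 60 evaluable per group; two-sided 0.05 with Bonferroni in section 3.2, so 0.05/6 = 0.0083 per pair; one SD, printed as −0.6 and read as 0.6 kg/m².

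**Inputs assumed.** The SDs of change at weeks 4 and 8 and the within-person correlation are not in the protocol. They are varied below.

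**The plan's own figures.** The protocol states no week-12 standard error or false-positive rate to reproduce. Its dropout step does reproduce: 60 / (1 − 0.20) = 75 and 4 × 75 = 300. The 60 does not follow from the printed inputs, which give 28 per group at 0.05/6. That is a separate matter and has no bearing here, because type I error depends only on the ratio of the SDs across visits.

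**Method.** AR(1) was fitted by likelihood to each assumed covariance, with a free mean for each group and visit. With R = model SE / true SE at week 12:
- R = √(model variance at week 12 / true variance at week 12)
- type I error = 2 × [1 − Φ(z × R)], with z = 1.960 at 0.05 and 2.638 at 0.05/6

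**One case by hand: SD proportional to √time.** The SDs are 0.35, 0.49 and 0.60, so the variances are 0.12, 0.24 and 0.36, with mean 0.24.
- R = √(0.24 / 0.36) = 0.816.
- True SE of a group difference = 0.60 × √(2/60) = 0.110; the model reports 0.110 × 0.816 ≈ 0.089.
- At 0.05: 1.960 × 0.816 = 1.600, giving 0.110.
- At 0.05/6: 2.638 × 0.816 = 2.154, giving 0.031.

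**Homogeneous AR(1) on change scores.** The ranges cover several assumed correlations. The last column is simulated (4 arms × 60, 3,000 runs per scenario).

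| Assumed SD, weeks 4 / 8 / 12 | R | Error at 5% | Error at 0.05/6 | Family-wise, 6 pairs at 0.05/6 |
|---|---|---|---|---|
| 0.60 / 0.60 / 0.60 | 1.00 | 5.0% | 0.8% | 4.4% |
| 0.48 / 0.55 / 0.60 | 0.91 | 7.5% | 1.7% | 8.4% |
| 0.35 / 0.49 / 0.60 (√time) | 0.82 | 11.0% | 3.1% | 12.8–13.8% |
| 0.20 / 0.40 / 0.60 (linear) | 0.73 | 15.0–15.5% | 5.3–5.6% | 20.8–22.0% |

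The simulated per-comparison error at 5% agreed: 5.0%, 7.9%, 10.8–11.1% and 14.7–15.5%. Linear growth with a little measurement error (R = 0.745) gives 2 × [1 − Φ(1.960 × 0.745)] = 14.4%. Adding a random participant intercept leaves the table unchanged, because the variance is still constant over visits.

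**Heterogeneous ARH(1) on change scores.** R is 0.97 to 1.00 and the error at 5% is 5.0–5.7% in every scenario.

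**Homogeneous AR(1) on raw BMI at weeks 0, 4, 8 and 12, with change as a contrast.** With growing spread, an SD of change of 0.9 at week 12 and measurement error of 0.1 to 0.3, R ran from 0.63 to 1.19. With the four patterns in the table and an assumed baseline SD of 3, R ran from 0.71 to 1.60 and the error at 5% from 16% down to 0.2%. The direction depends on the unknown covariance.

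**Unstructured covariance on change scores.** In 6,000 simulated trials (4 arms × 60, SD of change 0.9 at week 12, measurement error 0.15, spread growing by random slopes, random walk or a mix), the error at 5% was 4.3–5.2%. AR(1) on the same data gave 10.8–13.5%.

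**Limits.** The table and its simulations used complete data and left out age, sex and the planned multiple imputation. The effect of the 20% dropout on these figures was not examined.

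**The case against.** A reader might infer that the protocol forces equal variances, that the week-12 standard error is therefore too small, and that false positives roughly double. The text does not support this. An autoregressive correlation matrix describes correlations and is silent on variances. ARH(1) fits the same words and is available in PROC MIXED, and the unnamed random effects could include a participant slope, which lets the variance grow. Section 3.2 gives a single SD, so growth of the spread is plausible but is not a fact from the document. Doubling is one point in a range that starts at no inflation. If raw BMI is the response, the test can even be conservative. All of this stands, and it is why the point is conditional.

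A reader might also infer that two primary tests have been planned. The general linear model sentence speaks of study outcomes in general and is paired with a chi-squared test for categorical variables, whereas the mixed model is tied by name to change in BMI. Section 16.1 lists change in BMI among the study outcomes, so the overlap needs a clarifying line, but the text does not establish a second primary test. The unnamed random effects are likewise a point for clarification and do not show an error in the standard error.

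Finally, variance options, degrees of freedom and fallback structures commonly belong in a statistical analysis plan, which is not at hand. That would answer a complaint about silence. Here, though, the protocol has itself chosen a restrictive structure for the primary model.

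**Conclusion.** The point holds in conditional form. The protocol commits its primary model to an autoregressive structure with no stated protection if that structure is wrong. Under homogeneous AR(1) on change scores, the week-12 standard error is correct with equal spread at all visits and about 9%, 18% or 27% too small under the mild, square-root and linear growth assumed here. The matching type I errors at 5% are about 7.5%, 11% and 14–15%. Under ARH(1) little is wrong; under raw BMI the direction is open.

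Neither the direction nor the size can be read from the protocol, because it gives no SDs by visit and does not define the response. The reason to act is that readings which all fit the wording lead to materially different primary P values, and a structure that avoids the dependence is available at almost no cost.

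**What to change.** In section 16.2:
- Replace the autoregressive structure with an unstructured within-participant covariance for the scheduled visits, with Kenward-Roger degrees of freedom.
- State the repeated response: change at weeks 4, 8 and 12, or BMI at all four visits with change as a contrast.
- Name the random effects or delete the phrase; with an unstructured covariance none is needed.
- Name the week-12 group contrasts from this model as the primary test of change in BMI, and label any general linear model of that outcome a sensitivity analysis.

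ARH(1) or a robust standard error would also largely meet the concern on change scores, but with only three visits there is little reason to settle for a restricted structure.

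The cost is one covariance option and a few sentences. Three visits need 3 × 4 / 2 = 6 covariance parameters instead of 2, which is small against 300 participants. If BMI at four visits is modelled, the number is 4 × 5 / 2 = 10. Intervals may be slightly wider.

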3.1. Overall designs

This study is a randomized, multiple-center, parallel group, controlled clinical trial. After screening, all eligible trial participants will be randomly assigned to NC

group, LC diet group, CR diet group and LC+CR diet group (**Figure 1**) for 12 weeks with an allocation ratio of 1:1:1:1. A total of 300 participants will be enrolled. The study will be conducted in the following 13 hospitals in Guangdong Province, China:

- Zhujiang Hospital, Southern Medical University, Guangzhou;
- Huizhou Central People's Hospital, Huizhou;
- Qingyuan People's Hospital, Qingyuan;
- The Third Affiliated Hospital of Guangzhou Medical University, Guangzhou;
- DONGGUAN KANGHUA HOSPITAL, Dongguan;
- Hexian Memorial Affiliated Hospital of Southern Medical University, Guangzhou;
- Guangdong Provincial People's Hospital, Guangzhou.
- Guangdong Second Province Central Hospital, Guangzhou;
- Dongguan People's Hospital, Dongguan;
- Affiliated Hospital of Guangdong Medical University, Zhanjiang;
- The First People's Hospital of Shunde, Shunde;
- The Eighth Affiliated Hospital, Sun Yat-Sen University, Shenzhen;
- Shaoguan First People's Hospital, Shaoguan.

• Figure 1. The schedule for screening

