3.2. Statistical power and sample size

The study will enroll 300 participants, who will be randomly allocated to four groups with an equal number of individuals per group:

- NC group
- LC diet group
- CR diet group
- LC+CR diet group

The primary outcome (BMI) will be compared between any two groups at 12 weeks. The sample size calculation was based on the following assumptions:

- Statistical power 85%
- Significance level of 0.05 for the Bonferroni correction of multiple comparisons using a 2-tailed test
- Detectable effect size of BMI = $-0.6 \text{ kg/m}^2[25-28]$
- Standard deviation of BMI = $-0.6 \text{ kg/m}^2[25-28]$

Thus, 60 subjects in each group are required. Assuming a dropout rate of 20%, we will recruit 300 participants and randomly allocate 75 subjects to each group in the proposed clinical trial.

4. Inclusion and Exclusion Criteria

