6.1. Randomization

Randomization will be conducted by Department of Bio-Statistics, Southern Medical University, China. Patients will be randomly assigned to NC group, LC diet group, CR diet group or LC+CR diet group using a block design. The randomization scheme is generated and concealed until an eligible participant is ready to be randomized. Prior to randomization, the study coordinator should confirm that all screening procedures have been completed, the participant meets all eligibility criteria, and all required baseline data have been collected. Any individual lacking required documents and data will not be randomized.

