10.2. Methods

A. Questionnaire

Demographic information: A self-report demographic questionnaire will be used to collect participant characteristics at baseline, including age, race/ethnicity, socioeconomic status (employment, education, and income), internet usage, and health status.

Medical history: Medical history including medication used will be self-reported by participants at the screening visit and subsequent follow-up visits. The medical recordings will be reviewed at times to ensure all the data are complete.

Diet: Three 24-hour dietary recalls will be conducted at baseline and during follow-up visits. Nutrient intake will be calculated using the China Food Composition table.

Physical activity: Physical activity will be recorded for 3 continuous days by Mi Band 2 Smart Bracelet (Xiaomi, Beijing, China).

B. Clinical examination

B1. Weight, waist circumference, and blood pressure

Height will be measured to the nearest 0.5 cm at baseline and follow-up visits using a wall-mounted stadiometer. Body weight will be measured to the nearest 0.1 kg in duplicate at each visit using a digital scale with participants dressed in light indoor clothes and without shoes. A gulick tape measure will be used to obtain duplicate measurements of waist and hip girths to the nearest 0.1 cm. Blood pressure will be measured in triplicate at each visit using the Omron HEM-907-XL automated sphygmomanometer. Participants will avoid exercise, smoking, coffee or tea for 30 minutes. Participants will be seated quietly for 5 minutes before measurement.

B2. Body composition

The bioelectrical impedance method will be used to measure body fat content using an IOI353 Body Composition Analyzer(Jawon Medical, Gyeongsansi, South

Korea) to evaluate the body fat, body muscle.

C. Biochemical tests

Overnight blood samples and spot urine will be collected to measure metabolic risk actors (plasma glucose, insulin, triglycerides, total cholesterol, LDL- and HDL-cholesterol, liver enzymes, and uric acid) using standard methods at the clincial laboratory of each subcenter.

11. Baseline and Follow-up Visits

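### The covariates fixed for the primary BMI model omit baseline BMI, which gives up a modest amount of precision; the random effects, centre and the height used for BMI should be settled in the same revision

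*Protocol*

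**What the plan says.** Protocol section 16.2 models change in BMI with a mixed-effects model for repeated measurements and an autoregressive correlation. The fixed effects are spelled out: "intervention group, time, and their 2-factor interactions, age, sex will be assumed to be estimable fixed effects". Baseline BMI is not among them, and neither is centre. The same sentence says that variables will be random effects, but names none.

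The primary outcome in section 8.1 is "Changes in BMI from baseline at 12 weeks after intervention". Section 4.1 admits anyone with a BMI of 24 kg/m² or more and sets no ceiling. Section 6.1 bars randomisation until the required baseline data are in, so a baseline BMI exists for every participant.

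On centre, section 3.1 states: "The study will be conducted in the following 13 hospitals in Guangdong Province, China". Section 6.1 states: "Patients will be randomly assigned to NC group, LC diet group, CR diet group or LC+CR diet group using a block design". It does not mention stratification by centre.

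On height, section 10.2 states: "Height will be measured to the nearest 0.5 cm at baseline and follow-up visits using a wall-mounted stadiometer". Sections 11.4 to 11.6 schedule it again at weeks 4, 8 and 12. No section says whether follow-up BMI uses the height read at that visit or one fixed height.

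**The concern.** A baseline value of the outcome is usually the first covariate to consider in a model for change, because people who start higher tend to lose more in absolute terms. Here age and sex are in the model and baseline BMI is not. The protocol does not leave this open: it states a list, so a later analysis plan that added baseline BMI would be departing from the protocol.

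What is at stake is the width of the confidence intervals for the group differences in the primary outcome, and the same for each secondary outcome. Two neighbouring gaps bear on the same precision. The random effects are unnamed, so the role of centre cannot be read from the text. The source of height in follow-up BMI is also undefined, although adult height does not change over 12 weeks and each re-reading can only add noise.

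**Working it through.** **Inputs from the protocol (section 3.2):** difference 0.6 kg/m²; SD 0.6 kg/m² (printed with a minus sign, taken here as the SD of change); power 85%; two-sided 0.05 with Bonferroni; 60 evaluable per group. "The primary outcome (BMI) will be compared between any two groups at 12 weeks" implies six pairs, so alpha = 0.05/6.

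**The plan's own figure.** n per group = 2 × (SD/difference)² × (z for alpha/2 + z for power)² = 2 × 1 × (2.638 + 1.036)² = 27.0, rounded up to 28, not 60. An SD of about 0.89 would give 60. That mismatch is a separate matter. Here it only means that results are needed at an SD of 0.6 (as printed) and near 0.9 (as implied by 60 per group).

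**Baseline BMI, equal variance at baseline and week 12.** The baseline SD is not in the protocol; 2 to 4 kg/m² is assumed.
- Correlation of the two BMI values: rho = 1 − SDchange²/(2 × SDbaseline²).
- Share of change-score variance removed: (1 − rho)/2 = SDchange²/(4 × SDbaseline²).
- SD of change 0.6: 0.36/16 = 2.3% (baseline SD 2) to 0.36/64 = 0.6% (baseline SD 4).
- SD of change 0.9: 0.81/16 = 5.1% to 0.81/64 = 1.3%.
- In participants out of 60: 0.3 to 1.3 at SD 0.6; about 0.8 to 3.0 at SD 0.9.

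**Baseline BMI, loss proportional to BMI (assumed 5%).** The explained SD is 0.05 × 2 = 0.10 to 0.05 × 4 = 0.20.
- SD of change 0.6: 0.01/0.36 = 3% to 0.04/0.36 = 11%.
- SD of change 0.89: 0.01/0.79 = 1% to 0.04/0.79 = 5%.

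**Effect on intervals and power.** Width scales with the square root of the remaining variance: √0.994 = 0.997, √0.949 = 0.974 and √0.889 = 0.943. Intervals therefore narrow by 0.3% to 2.6% under equal variance, and by at most 5.7% under proportional loss. At 60 per group and alpha 0.05/6, power is already 99.8% at SD 0.6. At SD 0.9 it rises from 84.5% to between 85.0% and 86.6% under equal variance.

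**Chance imbalance.** A one-standard-error imbalance in baseline BMI at 75 per group shifts the group difference by r × SDchange × √(2/75). With the largest r above (√0.11 = 0.33) and SD 0.6, that is 0.33 × 0.6 × 0.163 = 0.03 kg/m², about 5% of the 0.6 target.

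**Centre.** 300/13 is about 23 participants per hospital. With an assumed intraclass correlation of 0.01 to 0.05, a centre term removes 1% to 5% of variance. Power at SD 0.89 goes from 85.4% to between 85.8% and 87.5%.

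**Height, if visit heights were used (assumed BMI 28, height 165 cm).**
- Sensitivity: 2 × 28/165 = 0.339 kg/m² per cm.
- Rounding SD: 0.5/√12 = 0.144 cm.
- Added SD of change: √2 × 0.339 × 0.144 = 0.069 kg/m².
- Added variance: 0.069²/0.36 = 1.3% at SD 0.6; 0.069²/0.79 = 0.6% at SD 0.89.

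This treats the two rounding errors as independent; readings that round the same way cancel. With an assumed reading-error SD of 0.25 to 0.5 cm on top, the added variance is 5% to 17% at SD 0.6 and 2% to 8% at SD 0.89. The protocol gives no figure for reading error.

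**The case against.** The strongest reply is that nothing here is an error. The outcome is change, so each participant's baseline already enters by subtraction; randomisation keeps the comparison unbiased; and an unadjusted change-score test is valid. A full covariate list is often left to the analysis plan, which is not at hand. At the printed SD of 0.6, power is so high that adjustment hardly moves it. Most of this stands, and it limits the point to precision. It does not remove the point: subtraction does not take out the association between baseline and change, and the protocol has written a list rather than deferred one.

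Several stronger readings are tempting, and the documents do not support them:
- **Centre is left out.** It is not a listed fixed effect, but the random effects are unnamed, so a random centre term is neither stated nor excluded.
- **Follow-up BMI is built on re-measured height.** The schedule allows this, but no section defines the calculation.
- **A 0.5 cm step is worth 0.17 kg/m², 28% of the target.** This sets one person's rounding against a difference in group means. At 60 per group, rounding contributes 0.069 × √(2/60) = 0.013 kg/m² to the standard error as a separate component.
- **Height error biases the result because staff are unmasked.** The trial is open-label (section 6.2), but section 17 calls the technologists blind to allocation, perhaps only those doing body composition. No section says who reads height. Without error that differs between groups, the effect is noise.
- **Week-12 BMI levels are compared with no use of baseline.** Section 3.2 taken alone could be read so, and an assumed SD of 3 kg/m² would then give about 6% power. Sections 8.1, 16.1 and 16.2 all name change.

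**Conclusion.** The point holds as one of modest precision. Section 16.2 states a closed list of fixed effects, and baseline BMI is missing from it. The cost is roughly 1% to 5% of residual variance under equal variances (baseline SD 2 to 4 assumed, SD of change 0.6 to 0.9), and up to about 11% if loss is proportional to BMI at an assumed 5%. It introduces no bias and does not invalidate the test, and chance imbalance is largely dealt with because the outcome is change.

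The centre and height items are clarifications to make alongside. Centre is worth perhaps 1% to 5% of variance on an assumed intraclass correlation. A fixed height is worth about 1% from rounding at SD 0.6, and more only if there is reading error, which the protocol does not quantify.

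**What to change.** In section 16.2:
- Add baseline BMI and its interaction with visit to the primary model, and the matching baseline value to the model for each secondary outcome.
- Name the random effects, and enter centre as a fixed or a random term. If fixed, settle in advance how very small hospitals are pooled.
- Define BMI at every visit from a single pre-randomisation height, and say which reading that is. Height need not be dropped from the follow-up visits.

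The cost is wording and a few parameters. With three follow-up visits, baseline BMI and its interaction take 3; centre takes 12 if fixed or 1 variance component if random. That makes 15 or 4 in all, against 300 participants. No new measurement is needed and the visit schedule is unchanged.

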However, previous studies have examined the effects of low-carbohydrate, energy deficit diet and calorie-restricted, low-fat diet on weight loss, but most of these trials did not compare the weight loss effects of a calorie-restricted diet alone (calorie-restricted, high/moderate-carbohydrate) with a low-carbohydrate diet alone (low-carbohydrate, non-calorie-restriction). In addition, these studies did not provide evidence that a combination of low-carbohydrate and calorie-restricted diet was more effective for weight loss and reducing metabolic risk factors than calorie-restricted diet or low-carbohydrate diet alone. Therefore, the effects of low-carbohydrate and calorie-restricted diet on weight loss and metabolic risk factors in overweight/obese adults need to be tested in future clinical studies.

2. Specific Aims

In this study, we aim to test the effects on weight loss in overweight/ obese adults by a combination of LC diet and CR diet. We propose to conduct a 12-week clinical trial to evaluate the effects of or LC and CR diet on weight loss. We hypothesize that a combination of LC and CR diet would have a greater weight loss and favorable metabolic effects than LC diet and CR diet alone in overweight/obese adults.

The primary specific aims are:

- 2.1. To test the effect of LC+CR diet over 12 weeks on changes in BMI compared to LC diet and CR diet alone;
- 2.2. To test the effect of LC diet over 12 weeks on changes in BMI compared to CR diet;
- 2.3. To test the effect of LC+CR diet, LC diet and CR diet alone over 12 weeks on changes in BMI compared to the NC group.

The secondary specific aim is:

2.4. To compare the effect of LC+CR diet, LC diet and CR diet control on waist circumference, body fat, and metabolic risk factors.

3. Research Design and Methods

[figure not shown]

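### The Bonferroni correction that section 3.2 uses to size the six primary BMI comparisons is not carried into the analysis rule in section 16.2

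*Protocol*

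**What the plan says.** Three parts of the protocol bear on this.

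- **Section 2, primary aims.** Aim 2.1 reads "To test the effect of LC+CR diet over 12 weeks on changes in BMI compared to LC diet and CR diet alone". Aim 2.2 reads "To test the effect of LC diet over 12 weeks on changes in BMI compared to CR diet". Aim 2.3 sets each of the three diets against NC. All three are listed as primary, and none is ranked above another.
- **Section 3.2, sample size.** "The primary outcome (BMI) will be compared between any two groups at 12 weeks", and among the assumptions: "Significance level of 0.05 for the Bonferroni correction of multiple comparisons using a 2-tailed test". The number of comparisons that the correction divides by is not given.
- **Section 16.2, analysis.** A mixed-effects model supplies the treatment effects and the tests between treatments. The decision rule is "P-value <0.05 will be considered as statistically significance". Results are reported as follows: "Data will be presented as least-squares means with 95% confidence intervals (CIs)". The section names no multiplicity adjustment, no order of testing and no gatekeeping overall test.

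**The concern.** The correction appears where the trial is sized and is absent where the result is declared. A reader who follows section 16.2 alone would compare each of six primary P values with 0.05. A reader who starts from section 3.2 would compare each with a much smaller threshold, or would adjust the P values first. A comparison with a raw P value between 0.0083 and 0.05 would be a positive primary result for the first reader and not for the second.

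The protocol should settle this before the data are seen. The trial is open-label (section 6.2), and any of the six comparisons can be presented as a primary finding. The stated hypothesis, that the combined diet beats each single diet, rests on two of them.

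**Working it through.** **Number of primary comparisons.** Aim 2.1 gives 2 (LC+CR against LC, LC+CR against CR), aim 2.2 gives 1 (LC against CR), and aim 2.3 gives 3 (each diet against NC). The total is 2 + 1 + 3 = 6. Four arms have 4 × 3 / 2 = 6 pairs, so the aims cover every pair, as section 3.2 says.

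**The plan's own figure.** Inputs from section 3.2: difference 0.6 kg/m², SD 0.6 kg/m² (printed with a minus sign; the positive value is used), power 85%, two-sided test. The normal-approximation formula is n per group = 2 × SD² × (z for alpha + z for power)² / difference².

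- At 0.05/6: 2 × (2.638 + 1.036)² = 27.007, so 28 per group (29 with the t distribution).
- At 0.05: 2 × (1.960 + 1.036)² = 17.96, so 18 per group (19 with the t distribution).

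Neither gives the stated 60. Divisors of 1, 3, 4, 5, 6 and 12, one- and two-sided, gave 15 to 31. An SD of 0.6 / (√(2/60) × 3.675) = 0.894 would be needed for 60 per group at 0.05/6. The dropout step does reproduce: 60 / 0.8 = 75 per group, 300 in total. The printed inputs therefore do not show which divisor was used. That is a separate problem in section 3.2. It matters here only because the divisor of 6 has to be inferred from the number of comparisons.

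**Family-wise error.** The six comparisons share arms, so they are correlated, and treating them as independent would overstate the error. For k equal arms of equal size, the chance that at least one pairwise t test is significant is the upper tail of the studentized range: P(Q with k groups and df degrees of freedom > √2 × t critical). With 60 evaluable per group, df = 4 × 60 − 4 = 236. Equal variances and one week-12 comparison per pair are assumed.

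| Rule per comparison | t critical | √2 × t | No arm differs (k = 4) | Three diets equal, NC differs (k = 3) |
|---|---|---|---|---|
| P < 0.05 | 1.970 | 2.786 | 20.2% | 12.2% |
| P < 0.05/6 = 0.0083 | 2.661 | 3.763 | 4.1% | 2.3% |

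A simulation of 400,000 trials gave 20.1% and 4.1% with no difference between arms, and 12.1% for three equal diets at P < 0.05. With 75 per group (df = 296) the 20.2% becomes 20.3%, so the result hardly depends on the sample size, and the assumed SD does not enter it.

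For reference, six independent tests would give 1 − 0.95⁶ = 26.5%, and the plain sum is 6 × 0.05 = 30%. Neither figure applies to these correlated comparisons.

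**The case against.** The strongest reply is that the two sections do not strictly contradict each other. Section 16.2 never calls its P values unadjusted. Bonferroni-adjusted P values are compared with 0.05, so both sections can be followed at once. The method is named in section 3.2, and the statistical analysis plan, which was not available, may spell out how it is applied. This much stands: a reader might infer that the trial plans uncorrected primary tests, and the protocol does not establish that. What does not stand is that nothing needs changing. Section 16.2 does not leave the threshold to a later document. It fixes one, without the correction.

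Four further limits stand.

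- It is tempting to say that the chance of a false primary claim is 20% without condition. That figure needs per-comparison testing at 0.05 and no difference among all four arms. It falls to about 12% if the diets are equal but differ from NC, and if all four arms differ from one another there is no true null hypothesis to reject falsely. An overall F test as a gate would hold the all-arms-equal error at 5.0% in simulation, but section 16.2 states no such gate.
- The 95% confidence intervals might be taken as proof of uncorrected testing. The sentence is about presenting least-squares means. Such intervals around arm means are compatible with corrected tests between arms.
- It cannot be confirmed that 0.0083 was the sizing threshold, because 60 per group does not follow from the printed inputs.
- A different procedure such as Holm, or a relabelling of the secondary outcomes, would go beyond the gap between the two sections.

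**Conclusion.** The point holds as a gap between the sizing section and the analysis section. All six pairwise BMI comparisons are primary, section 3.2 relies on a Bonferroni correction for them, and section 16.2 gives a 0.05 rule that does not carry it.

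If that rule is applied to each comparison, the family-wise error is about 20% with no difference between arms and about 12% with three equal diets that differ from NC. The corresponding figures with Bonferroni over six are about 4% and 2%. The 12% falls entirely on the diet-against-diet comparisons, which include the main hypothesis. These figures rest on equal arms, equal variances and one week-12 comparison per pair.

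The gap should be closed before analysis, because it determines whether a primary result is declared positive.

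**What to change.** In section 16.2, state that the six week-12 between-group BMI comparisons under aims 2.1 to 2.3 are tested with the Bonferroni correction named in section 3.2: each at two-sided 0.05/6 = 0.0083 or, equivalently, with Bonferroni-adjusted P values compared with 0.05. State that those six differences are reported with 99.17% confidence intervals (1 − 0.05/6 = 0.9917), so that tests and intervals agree. In section 3.2, state the divisor. If the statistical analysis plan already says this, a cross-reference in 16.2 is enough.

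The cost is a sentence or two of text and a stricter threshold per comparison than 0.05. On the printed inputs this needs 28 to 29 per group, below the planned 60. If the SD is nearer 0.89, 60 per group gives the planned 85% power at 0.0083, and a larger SD would give less. Since section 3.2 says that the sizing allowed for Bonferroni, the stricter threshold is in line with the stated design. Whether power is fully preserved can be confirmed only once the divisor and SD are stated correctly.
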